The aim of this registry is the prospective collection of data on the course of patients with Tofacitinib / biologics therapy in the "Real World Setting" to get insights in efficacy and safety which is relevant for the selection of the respective drugs in therapy.

The primary endpoint is steroid-free remission (remission: partial Mayo score ≤ 1 plus a bleeding subscore of 0) in the inductionphase (week 16). For this endpoint it will be only captured if there is a current use of steroids at the time of the visit. So the patient will be asked for current steroid use at time of visit at week 16 and if he has received steroids within the last 4 weeks prior to time point of the visit. As there is no common standard or definition of this endpoint in daily practice this is the most appropriate way to collect this data in non-interventional observational research.

Secondary registry objectives:

The collection of secondary objectives will be done under "Real World Conditions" to the extent that normal ongoing therapy requires normal treatment control.

1. Online documentation of safety and efficacy in induction and maintenance therapy including the occurrence of serious side effects (e.g., death, tumor, tuberculosis, severe infections, or side effects leading to hospitalization)
2. Efficacy (response: partial Mayo Score reduction of ≥ 3 accompanied by a decrease of at least 30% from baseline and remission: partial Mayo score ≤ 1 plus a bleeding subscore of 0) of induction therapy (week 8 and 16) and maintenance therapy (months 6 to 24) and efficacy (response and remission) in different subpopulations, e.g. based on a previous biologic therapy or not.
3. Obtaining health economic data in UC patients on Tofacitinib / biologics therapy (hospitalization, disability, treatment costs, quality of life, early retirement).
4. Obtaining data of the course from UC patients with a new therapy (Tofacitinib / biologics) related to treatment strategy and psychosocial impairments

Data with regard to additional registry objectives (supplementary subgroup analyzes), will only be captured in the normal routine in the course of UC-patients' treatment and in connection with routinely planned contacts at the ibd-center:

This is a non-interventional, observational registry, where patients are treated only regarding the following rules:

- The medicinal product is prescribed in the usual manner in accordance with the approved label,

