- The assignment of the patient to a particular treatment has to be done in advance to and independently from the inclusion into this NIS. The decision should be only led by the medical need of the patient and pure medical decision of the treating physician. The in- and exclusion criteria for this registry will be exclusively based on the Summary of Product Characteristics (SmPC).
- The timeframes for visits are non-binding suggestions on the base of recommended timeframes in the SmPC or standard of care procedures.
- No additional diagnostic or monitoring procedures beyond respective recommendations in the SmPC or standard of care procedures will be applied to patients and epidemiological methods are used for the analysis of collected data.

The safety and efficacy of induction and maintenance therapy of Tofacitinib and other biologics are assessed in several relevant subgroups of UC patients. Most planned analyzes are descriptive:

1. Safety and efficacy of Tofacitinib in comparison with other biologics: comparison of groups with different pretreatments (e.g., biologics-naïve and biologics-experienced UC-patients or also compared to immunosuppressive drugs in pre-treatment).
2. Effects of Tofacitinib and other biologic therapies on the number of proctocolectomies and hospitalizations

3. Treatment dynamics according to the mode of treatment over time (e.g., change in proportion of Tofacitinib and first-time use of biologics in biologic naive UC patients)

4. Registry design

This is an Investigator-initiated non-randomized, non-interventional observational prospective long-term research (IIR) as part of the normal treatment of UC patients for the safety and efficacy of Tofacitinib / biologic therapies. As of 01st July 2019, UC patients who have been provided Tofacitinib / biologics for UC according the respective label by the treating physician may be prospectively included in an online database by the participating study centers by 31st March 2021.

An interim analysis is planned at the end of patients' recruitment with respect of the induction phase (week 16) for October 2021 with a first publication of the data in a peer-reviewed journal (e.g., JCC, GUT, UEG Journal).

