Up to 480 patients (including about 360 UC patients with Tofacitinib and about 120 UC patients with biologics) will be included in the online documentation. A specification to the study centers regarding the group inclusion (patients treated with Tofacitinib (group 1) or a biologics (group 2)) will not be made; this means, each study center can include patients in both groups.

We assume that approximately 20-30% of Tofacitinib patients will be biologic-naïve UC patients, many of whom will represent early disease patients (< 2 years after first diagnosis).

5. Registry conduction

Data will be documented in an online registry-like database. Follow-up documentation in an abbreviated online follow-up form takes place every 6 months during the prospective registry (M6-M24) according to the normal planned clinical visits. In group 1 and 2, the induction phase, (if patient contact occurs within the framework of normal care) will be followed by up to three additional visits (W2, 8, 16) in the first three months after initiation of Tofacitinib / biological therapy. Any medication side effects are also recorded online in an AE / SAE sheet. About 15% of documented cases are monitored by in-house or on-site monitoring. In addition, in the context of the usual care patient contacts, the supervising physician carries out a prospective documentation of the course of the disease at intervals of approximately six months.

6. Selection of registry population

The diagnosis UC is made in accordance with current DGVS/ECCO UC guidelines. Patients for whom the indication of Tofacitinib / biologics therapy has been submitted for medical indication by the treating physician can be entered in the registry. The therapy decision is made by the physician, regardless of and in advance to a potential registry participation.

There are the following inclusion and exclusion criteria:

Inclusion Criteria:

- Patients with moderate to severe Ulcerative Colitis aged 18-80 years at enrollment
- Written informed consent is given

Exclusion Criteria:

- Malignant disease in history (except for non-melanoma skin cancer)
- Any contraindication according to the SmPC of the respective medication

There are two subpopulations:

1. UC-patients (age at enrollment: 18-80 years) receiving a newly introduced Tofacitinib therapy (n=360). Previous treatment(s) with biologics or immunosuppressants is (are) permitted. About 20-30% of the Tofacitinib patients will biologic-naiv.

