2. UC-patients (age at enrollment: 18-80 years) receiving a newly introduced biologics therapy (n=120). Previous treatment(s) with biologics or immunosuppressants is (are) allowed.

7. Criteria for selecting participating study sites

The investigator initiated non-interventional research (IIR) is conducted at sites in hospitals or gastroenterology practice sites that have special experience in the treatment of inflammatory bowel disease. Site selection will be directed by the principal investigator.

8. Sample size calculation, Data Monitoring, Data acquisition and statistical evaluation

Sample size calculation:

The sample size calculation is based on the achievement of the primary endpoint (steroid-free remission) at the end of the induction phase. The steroid-free remission rates between a tofacitinib therapy in "real word setting" are compared with a control group in an allocation ratio of 3:1. A total drop out rate of 10% is assumed.

Basic statistical determinations:

- Two independent groups
- Comparison of two unequal ratios to each other (proportions)
- Two-sided test problem (Fisher's exact test)
- Global alpha error of 5%.
- Power 80%
- No adjustment for multiple testing

Group allocation and acceptance of securities

The steroid-free remission rate in the control group is assumed to be 0.45.

The clinically relevant odds ratio (OR) for the primary endpoint was set to at least 1.9.

This results in the following remission rates:

Group 1: IBD on Tofacitinib proportion $p_1 = 0,61$

Group 2: IBD on control proportion $p_2 = 0,45$

Sample size:

Group	Percentage	Sample size	Sample size inclusive 10% „drop out“ Rate*
Tofacitinib	75%	325	360
Control	25%	108	120
Total	100%	433	480

Note: Due to rounding, deviations may occur in the table.

Data Monitoring: A spot-monitoring with full source data verification will be carried out in 10-15% of documented using internal, trained and certified monitors. A site monitoring plan will be drawn up by the principal investigator together with the sponsor. In the induction period, there will be an additional in-house/on-site data probability check. Selected high recruiting study centers will be subjected to an additional on-site monitoring supported by external monitoring personnel. Monitoring will start in a center when at least 10 patients will be recruited.

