Data acquisition will be done online on a central server (FORGA Solutions GmbH). Data transfer and evaluation is pseudonymized. Statistical evaluation will be done by FORGA Solutions, Berlin, with the support of the institutes of the principal investigators for specific additional issues and stratification with regard to the number of prior biologics therapies (an appropriate sample size analysis will be performed before each sub-analysis).

Data evaluation is also supported by the Competence Network Intestinal Diseases e.V.. The boxes in the online documentation form are equipped by input logic settings to prevent false entries. The cumulative data, especially the side effects reports, are sent by the study coordinator in a timely manner to the biologics companies funding the registry and semiannually for internal information.

Statistical evaluation will be performed by applying the descriptive methods in terms of frequency tables and statistical values, as average values, standard deviation and quantiles. As graphical methods bar diagrams will be shown with box-and-whisker-plots for quantitative data. Furthermore,

univariate significance tests and inferential statistical methods will be done supported by applicable two-sided asymptotic significance tests and confidence intervals, including chi-square test and Wilcoxon-W test and McNemar's test for comparison of dependent variables. During the analysis of evaluation criteria local significance levels of $\alpha=0.05$ will be controlled instead of global significance levels. No adjustment for multiple tests will be proceeded. Complete evaluation criteria will be exploratory analyzed with no proceeded testing of in advance formulated hypotheses. Accordingly, to these mentioned methods the obtained p-values will be interpreted in terms of Fisher's method: a p-value will be considered as a metric data and the effect is higher the smaller is the p-value. Missing data will not be replaced.

9. Duration of the registry

The registry is planned for a 3.75-year period as a longitudinal investigation. In consultation with study coordination personnel and the funding pharmaceutical company, the registry period may be extended to a longer period than 3.75 years.

10. Study flow of the registry

Starting from July 01th, 2019, patients with UC on a Tofacitinib therapy will be documented in a prospective online documentation form at the participating study sites.

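### The week-16 remission comparison sets no baseline partial Mayo condition and no limit from first dose to baseline score, so patients already in steroid-free remission can count as successes

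*Protocol*

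**What the plan says.** **Activity at entry.** The only activity criterion in Protocol Section 6 is "Patients with moderate to severe Ulcerative Colitis aged 18-80 years at enrollment". It names no score, no assessment date and no requirement that disease be active on the day of entry.

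**Start of therapy.** Section 6 describes group 1 as "receiving a newly introduced Tofacitinib therapy (n=360" and group 2 as "receiving a newly introduced biologics therapy (n=120". Section 5 counts the visits at weeks 2, 8 and 16 from initiation of therapy, and the flow chart in Section 11 puts baseline at time 0. The looser wording is in Section 4, where "UC patients who have been provided Tofacitinib / biologics for UC according the respective label by the treating physician may be prospectively included", and in Section 10, where "patients with UC on a Tofacitinib therapy will be documented in a prospective online documentation form". Section 10 also places the initial documentation at enrollment rather than at first dose. No section says how recent a new therapy must be.

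**Endpoint.** Sections 3 and 10 define the primary endpoint as steroid-free remission at week 16, with "remission: partial Mayo score ≤ 1 plus a bleeding subscore of 0". Steroid use is asked at that visit and for the four weeks before it. No change from baseline is required. The secondary response endpoint does need a fall of at least 3 points.

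**Baseline score.** The partial Mayo score is recorded at baseline (Sections 10 and 11) but used neither for eligibility nor for the primary endpoint.

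**The concern.** An endpoint that is a state rather than a change measures a treatment effect only if patients start outside that state. Nothing in the protocol ensures this. A patient with a score of 0 or 1, no bleeding and no steroids at entry meets the primary endpoint at week 16 by staying the same. That patient could never be a responder, because a fall of 3 points is impossible from a score of 1. Remission and response would then describe different populations without saying so.

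The timing gap works in the same direction. If the baseline score may be taken some time after the first dose, it can already reflect improvement, which also makes response harder to reach.

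Two things are at stake. Equal shares of such patients in both groups dilute the contrast. Unequal shares create a contrast that is not a drug effect. The second is a real possibility here because allocation is not randomized (Section 4) and the methods in Section 8 are univariate tests, which do not correct for a baseline imbalance.

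**Working it through.** **Inputs from Protocol Section 8.** Control rate 0.45, tofacitinib rate 0.61, odds ratio at least 1.9, allocation 3:1, two-sided Fisher's exact test at 5%, power 80%, evaluable numbers 325 and 108 (433 in total).

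**Step 1: reproduce the plan's figure.** The odds ratio is (0.61/0.39)/(0.45/0.55) = 1.91. The two-proportion formula with continuity correction gives 109 control and 327 tofacitinib, 436 in total, within 1% of the stated 433. Exact two-sided Fisher power at 325/108, by full enumeration, is 81.5%. The sample size arithmetic is sound and is not in question.

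**Step 2: assumptions.** The protocol gives no share of patients already in steroid-free remission at entry. Let f be that share and let 90% of them still meet the endpoint at week 16. Take 0.61 and 0.45 to apply to everyone else. The observed rate in a group is then (1 − f) × p + f × 0.9.

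**Step 3: equal shares, true rates 0.61 and 0.45.** For f = 10%: 0.9 × 0.61 + 0.1 × 0.9 = 0.639, and 0.9 × 0.45 + 0.1 × 0.9 = 0.495.

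| f in both groups | Tofacitinib | Control | Difference | Fisher power at 325/108 |
|---|---|---|---|---|
| 0% | 0.610 | 0.450 | 0.160 | 81.5% |
| 5% | 0.6245 | 0.4725 | 0.152 | 77.4% |
| 10% | 0.639 | 0.495 | 0.144 | 73.0% |
| 20% | 0.668 | 0.540 | 0.128 | 64.6% |

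**Step 4: unequal shares, no true difference (0.45 in both groups).** For 20% vs 5%: 0.8 × 0.45 + 0.2 × 0.9 = 0.540, and 0.95 × 0.45 + 0.05 × 0.9 = 0.4725.

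| f tofacitinib vs control | Tofacitinib | Control | Test rejects |
|---|---|---|---|
| 0% vs 0% | 0.450 | 0.450 | 4.4% |
| 10% vs 5% | 0.495 | 0.4725 | 6.3% |
| 10% vs 0% | 0.495 | 0.450 | 11.9% |
| 20% vs 5% | 0.540 | 0.4725 | 21.8% |

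**Step 5: what restriction does to power.** Removing the same shares leaves 325 × (1 − f) and 108 × (1 − f) patients with the rates back at 0.61 and 0.45. That is 309/103, 292/97 and 260/86 for 5%, 10% and 20%, with Fisher power 78.2%, 77.3% and 71.5%. In each case this is better than leaving those patients in, but below 81.5%, because the patients removed are not replaced.

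**The case against.** The protocol requires moderate to severe disease, on-label prescribing and a decision led by medical need, and Section 3 bases its criteria on the product label alone. Having no score cut-off is a legitimate choice in a non-interventional registry. This stands as far as enrollment goes, and it makes entry in remission less likely. It does not exclude it, because none of these conditions is tied to a measured score at entry.

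A reader might infer that entry is not tied to the first dose at all. The documents do not support that. New therapy, visits counted from initiation and a baseline at time 0 all link entry to treatment start. The wording in Section 4 fits the rule that treatment is chosen before inclusion, and the line in Section 10 may be only a loose summary. What is missing is the working rule: a definition of new therapy and a maximum interval.

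A reader might also infer that early failures never enter. That is speculation. Section 10 calls for consecutive enrollment, which works against it, although no rule excludes late entry.

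It is tempting to add the patient whose score is low at entry because of steroids. That example fails. If nothing changes, the patient is still on steroids at week 16 and fails the endpoint. Coming off steroids while keeping remission is an informative outcome.

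The sizes are conditional. If 0.61 and 0.45 already describe the mix of patients a registry enrolls, there is no power loss against the plan. The 20% vs 5% case is a large imbalance, and 10% vs 5% barely moves the error rate.

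Finally, analysis sets are often left to the SAP, which is not shown and could apply the restriction. The endpoint and the entry criteria are protocol content, however, and the protocol fixes both without a baseline link.

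**Conclusion.** The point holds in limited form. The protocol pairs an absolute week-16 endpoint with an activity criterion that has no score or date, and it sets no window from first dose to baseline score. Patients already in steroid-free remission can therefore count as successes without a treatment effect, and a difference in their share between the groups would bias the primary comparison.

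The size is unknown. Under the stated assumptions, equal shares of 5% to 20% cost about 4 to 17 percentage points of power (81.5% to 77.4% through 64.6%). Small imbalances do little harm, while larger ones raise the false-positive rate to between about 12% and 22%. The change should be made because the primary comparison is otherwise hard to interpret and the remedy is cheap. It is not evidence that the registry's result will be wrong.

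**What to change.** In the endpoint text of Sections 3 and 10, state that the primary week-16 comparison includes patients who

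- have a partial Mayo score documented at or before the first dose, or within a short fixed window that the protocol names; and
- do not already meet the full steroid-free remission definition at that baseline, meaning score, bleeding and steroid status together.

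Keep patients who are in remission on steroids. Define newly introduced therapy by the same window, and bring the wording of Sections 4 and 10 into line with Section 6. Record the first-dose date of the registry drug as its own field: Section 10 lists dosage under current medication and treatment period only under drug history. Ask the four-week steroid question at baseline as well, so that the same definition can be applied at both times. Report the share excluded in each group, and analyze all enrolled patients as a sensitivity analysis.

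The cost is wording, one date field and one baseline question, with no change to care, visits or enrollment. Some patients leave the primary denominator, with the power shown in Step 5 of the working.

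### Section 8's rule that a smaller p-value means a larger effect, with unadjusted 5% tests and strata by prior biologics, would let stratum size decide whether the drug effect seems to depend on pretreatment

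*Protocol*

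**What the plan says.** Several parts of the Protocol bear on this point.

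- **Aims.** Section 3, secondary objective 2, asks for "efficacy (response and remission) in different subpopulations, e.g. based on a previous biologic therapy or not". In the same section, item 1 of the planned analyses sets tofacitinib against other biologics with a "comparison of groups with different pretreatments", and gives biologic-naive and biologic-experienced patients as an example.
- **Stratum size.** Section 4 expects that "approximately 20-30% of Tofacitinib patients will be biologic"-naive. It gives no such share for the biologics group. Enrolment is capped at 480 (about 360 and 120), and the first analysis, of the induction phase, is set for October 2021, after recruitment ends in March 2021.
- **Stratified analysis.** Section 8 provides for stratification by the number of prior biologic therapies, with the promise that "an appropriate sample size analysis will be performed before each sub-analysis".
- **Tests.** Section 8 also says that "univariate significance tests and inferential statistical methods will be done supported by applicable two-sided asymptotic significance tests and confidence intervals" and that "local significance levels of $\alpha=0.05$ will be controlled instead of global significance levels", without adjustment for multiple tests.
- **Reading rule.** Section 8 then treats the p-value as a metric quantity: the smaller it is, the larger the effect is taken to be. It calls the whole evaluation exploratory.

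No passage says how the tofacitinib-biologics difference is to be compared between pretreatment strata.

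**The concern.** A p-value mixes effect size with sample size. The protocol expects the naive stratum to be roughly a quarter of the tofacitinib group and the experienced stratum about three quarters. If each stratum is tested at 5% and the p-values are read as effect sizes, the larger stratum will usually seem to show the larger effect, whatever the truth. Readers would then be told that tofacitinib's advantage depends on prior biologics when only the stratum sizes differ.

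This matters because section 3 says the registry's findings are meant to be relevant to the choice of drug, and sections 4 and 15 plan journal publication. The sample size step looks like a safeguard. For the induction analysis, however, it comes when the numbers are already capped and collected, and the protocol attaches no decision rule to it.

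**Working it through.** **Inputs from the Protocol.** Section 8: control remission rate 0.45, odds ratio (OR) 1.9, tofacitinib rate 0.61, two-sided 5%, Fisher's exact test for the design, 80% power, 3:1 allocation, 325 + 108 = 433 evaluable, 10% dropout. Section 4: 20-30% of tofacitinib patients biologic-naive.

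**Assumptions, not in the Protocol.** The naive share in controls equals that in the tofacitinib group (10% and 50% also tried). True remission rates are the same in naive and experienced patients. Two strata are used, although section 8 stratifies by number of prior biologics.

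**Step 1: reproduce the design.** The tofacitinib rate is (1.9 × 0.45/0.55) / (1 + 1.9 × 0.45/0.55) = 1.5545/2.5545 = 0.6085, stated as 0.61. The continuity-corrected formula gives 327 + 109 = 436, against the stated 433. Enumerated Fisher power at 325:108 is 81.5%. Dropout: 325/0.9 = 361 and 108/0.9 = 120, stated as 360 and 120. The design figures hold.

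**Step 2: power within strata when the effect is identical (0.61 vs 0.45).** Power is the sum of the product of the two binomial probabilities over all outcomes that the test calls significant. Discordance, meaning exactly one stratum significant, is P₁(1 − P₂) + P₂(1 − P₁). For the chi-square test:

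| Naive share | Naive n | Experienced n | Power naive | Power experienced | Exactly one significant |
|---|---|---|---|---|---|
| 20% | 65:22 | 260:86 | 25.6% | 73.7% | 61.6% |
| 25% | 81:27 | 244:81 | 31.3% | 71.6% | 58.1% |
| 30% | 98:32 | 227:76 | 35.5% | 68.9% | 55.5% |

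At 20%, for example: 0.256 × 0.263 + 0.737 × 0.744 = 0.067 + 0.548 = 0.616. Fisher's test gives 61.2%, 58.3% and 56.3%.

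**Step 3: apply the reading rule itself.** Under the same conditions, the experienced stratum has the smaller p-value in 72% (30% naive) to 81% (20% naive) of registries. With equal effects, a fair comparison would favour it in about half.

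**Step 4: vary the assumptions.** Discordance (chi-square, 20-30% naive in both groups) by true common OR:

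| OR | 1.0 | 1.3 | 1.5 | 1.7 | 1.9 | 2.2 | 2.5 | 3.0 |
|---|---|---|---|---|---|---|---|---|
| Exactly one significant | 9-10% | 23% | 39-40% | 51-54% | 55-61% | 51-61% | 40-54% | 25-40% |

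(The OR 1.9 column uses the unrounded rate of 0.609.) At OR 1.9 with half the controls naive, the figure is about 50%; with 10% of controls naive it is 67-72%. With three strata (0, 1, and 2 or more prior biologics, shares assumed), the strata are not all alike in significance in 72-73%.

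**Step 5: what an interaction estimate gives.** The variance of the log ratio of odds ratios is the sum of 1/(n·p·(1 − p)) over the four cells. At 25% naive: 0.0517 + 0.1496 + 0.0172 + 0.0499 = 0.2685, so SE = 0.518; over 20-30% naive, SE = 0.56 to 0.49. The 95% interval therefore runs a factor of exp(1.96 × 0.518) = 2.8 either side of the estimate. With identical effects, a 5% interaction test declares a difference in about 4.5-4.8% of simulated registries (400,000 runs). Its power for a true ratio of 1.9 is Φ(ln 1.9/0.518 − 1.96) = 23.5%, and 21-26% over the range. Power of 80% would need a ratio of about 3.9-4.8.

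**Step 6: the sample size step.** The design effect needs 433 evaluable patients. The naive stratum would have about 87 (65 + 22) to 130 (98 + 32), and the experienced stratum about 346 to 303. Neither reaches 433, and after March 2021 no calculation changes that.

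**The case against.** The strongest reply is that the protocol never says tofacitinib will be tested against biologics separately in each stratum, or that a difference will be claimed because one test is significant and the other is not. It says most planned analyses are descriptive, calls the evaluation exploratory, names confidence intervals and leaves room for inferential methods beyond the univariate tests. An interaction model may stand in an analysis plan that is not shown. Planned analysis 1 could also mean naive against experienced patients, which is not an interaction question. The sample size step carries no date, and section 15 plans evaluations while the registry runs.

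Much of this stands. Separate within-stratum tests are an inference, though a natural one. The absence of an interaction model would not be a finding on its own. A reader might also infer that secondary objective 2 will get a false answer. The text does not support that: the objective asks for response and remission in subpopulations, and rates with intervals answer it.

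What the reply does not remove is the reading rule, which section 8 states outright. Treating p-values as metric makes matters worse here, because it turns a difference in sample size into a difference in effect. Exploratory status does not make a p-value an effect measure. The objection about timing succeeds for sub-analyses in general but not for the induction analysis, which follows the close of recruitment.

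**Conclusion.** The concern holds as a badly fixed reading rule, conditional on that rule being applied to the drug comparison by pretreatment. At the protocol's OR of 1.9, with 325:108 evaluable and 20-30% naive in both groups, separate tests disagree in about 55-62% of registries although the effects are identical, and the experienced stratum has the smaller p-value in 72-81%.

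It is tempting to say that identical effects will look different in more than half of registries, full stop. The documents do not support that. The figure needs a true common OR of roughly 1.7 to 2.2 and similar naive shares in both groups, and the control share is not stated. Looking different here means one stratum significant and the other not; the estimates themselves differ significantly in only about 5%.

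The primary comparison is unaffected. The change should be made, but the trial does not depend on it.

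**What to change.** In section 8:

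1. State that drug effects by prior biologics (naive or experienced, and by number) are estimated in one model with a treatment-by-pretreatment interaction, and that stratum odds ratios are shown with 95% intervals.
2. State that a difference between strata is claimed only from the interaction estimate and its interval, never by comparing separate p-values.
3. Drop, for these analyses, the rule that a smaller p-value means a larger effect.
4. Replace the sample size analysis before each sub-analysis with the precision expected from the capped numbers: an SE of the log ratio of odds ratios of about 0.49-0.56, on the assumptions above. Deleting that clause alone would change no result.

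The cost is a few sentences and no new data, since drug history is already recorded at baseline (section 10, item 1.2). The downside is low interaction power, about 21-26% for a ratio of 1.9, so fewer subgroup claims will be possible. A wide interval must not be reported as evidence that the strata are alike.

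### The week-16 comparison between physician-selected groups is sized on a crude Fisher test, and only unadjusted tests are named to evaluate it

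*Protocol*

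**What the plan says.** **How groups form.** The design is non-randomised (protocol section 4). On treatment choice, section 3 says: "The decision should be only led by the medical need of the patient and pure medical decision of the treating physician". Section 6 places that choice before and apart from registry entry, and section 4 gives centres no instruction on which group to recruit.

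**What is sized.** Section 8 states that steroid-free remission rates on Tofacitinib "are compared with a control group in an allocation ratio of 3:1". The listed test is "Two-sided test problem (Fisher's exact test", at 5% alpha and 80% power. "The steroid-free remission rate in the control group is assumed to be 0.45", and the relevant OR is 1.9, giving 0.61 on Tofacitinib. The result is 325 + 108 = 433 evaluable patients, or 360 + 120 = 480 enrolled.

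**What is named for evaluation.** Section 8 says "univariate significance tests and inferential statistical methods will be done supported by applicable two-sided asymptotic significance tests and confidence intervals" and lists chi-square, Wilcoxon and McNemar tests.

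**Nearest text to adjustment.** Section 8 foresees support from the investigators' institutes "for specific additional issues and stratification with regard to the number of prior biologics therapies", with a sample size analysis before each sub-analysis. Section 3 mentions pretreatment where it lists subgroup assessments, and refers in general terms to epidemiological methods.

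**Status of the inference.** "Complete evaluation criteria will be exploratory analyzed with no proceeded testing of in advance formulated hypotheses" (section 8). Section 3 calls most analyses descriptive.

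**The concern.** When physicians choose the drug, the two groups can differ in prior treatment, disease activity, steroid use and disease duration, all of which may affect remission. A crude comparison attributes those differences to the drug. Section 4 expects 20-30% of Tofacitinib patients to be biologic-naive and gives no share for the biologics group, so balance cannot be presumed even on the factor the protocol itself singles out.

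The estimate matters because the primary objective in section 3 is to give insights relevant to drug selection, and the week-16 results are due for publication from the October 2021 analysis. Section 8 also reads a smaller p-value as a larger effect, so selection bias would feed directly into the reported strength of effect.

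**Working it through.** **1. Reproduce the planned size.** Odds at the control rate: 0.45/0.55 = 0.818. Times 1.9 = 1.555, so p1 = 1.555/2.555 = 0.6085 (printed as 0.61). Exact enumeration of the two-sided Fisher test gives power 0.807 at 325/108 and 0.798 at 324/108. The planned number therefore reproduces as a crude comparison and carries no allowance for adjustment.

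**2. Illustrate confounding by one factor, biologic-naive status.**

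- From the protocol: control rate 0.45; within-stratum OR 1.9 or 1 (no effect); Tofacitinib naive share 25% (midpoint of 20-30%); exact 3:1 split, 324/108.
- Assumed: naive-versus-experienced OR of 2 or 1.5; control naive share c of 10%, 25% or 50%.
- Stratum rates pN and pE are solved from c·pN + (1−c)·pE = 0.45 and odds(pN)/odds(pE) = 2 (or 1.5). The Tofacitinib rate is 0.25·pN + 0.75·pE, after multiplying each stratum's odds by the drug OR.

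Worked case, c = 50%, prognostic OR 2:

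- Control: pN = 0.535, pE = 0.365; 0.5 × 0.535 + 0.5 × 0.365 = 0.450.
- No drug effect: Tofacitinib rate 0.25 × 0.535 + 0.75 × 0.365 = 0.408; crude OR (0.408/0.592)/0.818 = 0.84.
- Within-stratum OR 1.9: naive odds 1.151 × 1.9 = 2.186, rate 0.686; experienced odds 0.575 × 1.9 = 1.092, rate 0.522. Tofacitinib rate 0.25 × 0.686 + 0.75 × 0.522 = 0.563. Crude risk difference 11.3 points, crude OR (0.563/0.437)/0.818 = 1.58.
- Standardised truth: pooled naive share (81 + 54)/432 = 31.25%; 0.3125 × (0.686 − 0.535) + 0.6875 × (0.522 − 0.365) = 15.5 points.

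Results, with rejection rates by exact Fisher enumeration:

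| Prognostic OR | Control naive share | Null crude OR | Null rejection | Crude OR if true OR is 1.9 | Power |
|---|---|---|---|---|---|
| 2 | 10% | 1.11 | 7.0% | 2.08 | 89% |
| 2 | 25% | 1.00 | 4.4% | 1.87 | 78% |
| 2 | 50% | 0.84 | 10.5% | 1.58 | 51% |
| 1.5 | 10% | 1.06 | 5.4% | 2.01 | 86% |
| 1.5 | 25% | 1.00 | 4.4% | 1.89 | 79% |
| 1.5 | 50% | 0.90 | 6.4% | 1.71 | 64% |

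At prognostic OR 2 the crude risk difference is 18.0, 15.5 and 11.3 points, against a standardised truth of 15.5 throughout. If both naive shares lie within 20-30%, the null OR stays between 0.93 and 1.07 and null rejection between 4.4% and 5.6%.

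**3. Test the remedy.** Logistic regression on group and naive status (simulation, prognostic OR 2, shares 10/25/50%) gives null rejection of about 5%, a median adjusted OR of 1.90-1.91 and a standardised risk difference of 15.5 points at each share. Power is 81%, 81% and 78%.

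**4. Price a fuller covariate set.** Let R² be the share of treatment choice explained by the covariates (assumed), with effective size n(1 − R²) from 325/108. R² = 0.1 gives 292/97 and Fisher power 0.766; R² = 0.2 gives 260/86 and 0.706. If a further 10% of patients lack a covariate, the sizes are 263/87 and 234/78, with power 0.715 and 0.669.

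**The case against.** The strongest reply is that this is detail for the statistical analysis plan. The list of tests is open-ended, section 8 allows inferential methods beyond the univariate tests, section 3 speaks of epidemiological methods, and nothing excludes adjustment. Fisher's test is only a sizing input. Pretreatment is also not ignored: section 3 sets out the comparison of Tofacitinib with other biologics by pretreatment, and section 8 foresees stratification by number of prior biologics. Comparing drugs within such strata would remove the imbalance illustrated above. Finally, the evaluation is labelled exploratory, and the illustration rests on assumed shares.

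Part of this stands. The open list is real, an analysis plan could add a model, and the exploratory label reduces the weight of error rates. The bias is small if the naive shares are close.

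It does not dispose of the point. The protocol is not merely silent: it sizes on a crude test and describes its significance tests as univariate. The pretreatment text sits with subgroups and sub-analyses, and the likeliest reading is that it does not govern the main comparison. Calling the analysis exploratory does not remove bias from an estimate. Naive status is also only one of several factors that may drive treatment choice.

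**Conclusion.** The concern holds and should be fixed. The sample size arithmetic is sound for a crude comparison; the weakness is that a crude comparison is what the protocol specifies for groups formed by clinical judgement. Followed as written, it gives a between-drug estimate that cannot be separated from patient selection.

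The direction and size of the bias cannot be derived from the protocol. In the illustration, a true OR of 1.9 shows as anything from 1.58 to 2.08, depending on an assumed control naive share of 10-50% and an assumed prognostic OR of 2. With equal shares this factor does no harm. Confidence is medium, because the real imbalance is unknown and an analysis plan that is not shown may add a model.

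**What to change.** In section 8, make the main between-group estimate of week-16 steroid-free remission a covariate-adjusted one, for example logistic regression with standardisation or propensity-score weighting. State the covariates before week-16 results are seen, choosing from what section 10 already records at baseline: number of prior biologics, prior immunosuppressants, partial Mayo score, steroid use, disease duration, involvement pattern and age. Report the adjusted risk difference and OR with 95% confidence intervals, and keep the crude test as supportive. Say whether the stratification by prior biologics applies to this comparison, that the 80% power refers to the crude test, and that unmeasured confounding remains.

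The cost is wording only, with no new data or patients, but precision falls. Adjusting for naive status alone costs little, while a fuller covariate set at the planned size leaves power of about 77% to 71% (R² 0.1 to 0.2). Because "Missing data will not be replaced", patients without a covariate would be lost from the model; a further 10% lost brings power to about 72% to 67%.
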